Secondary endpoint of efficacy is measured by response rate. Secondary endpoints of PK include C_{max}, CLT, AUC(TAU), C_{trough}, AI_AUC, and AI_C_{max}.

Exploratory endpoints include time to response, duration of response, and time to peak response.

Endpoints for the Long Term Extension Period

Primary endpoints of safety for the long-term extension period will be measured by AE, SAE, ECG, and laboratory abnormalities including safety biomarkers of d-Dimer and TAT.

The endpoint of efficacy is measured by response rate.

Analyses:

Demographics and Baseline Characteristics

Frequency distributions of gender and race will be tabulated. Summary statistics for age, body weight, height, and Body Mass Index (BMI) will be tabulated. Prior therapies will be listed and summarized for each dose.

Safety Analyses

All recorded adverse events will be listed and tabulated by system organ class, preferred term and treatment. Vital signs and clinical laboratory test results will be listed and summarized by treatment. Any significant physical examination findings, and clinical laboratory results will be listed. ECG readings will be evaluated by the investigator and abnormalities, if present, will be listed.

Efficacy Analyses

Platelet count and change from baseline will be listed for all treated subjects. Response status will be reported together with time to respond, time to peak response, and duration of response. Response rate will be provided by cohort and treatment phase (response phase or remission phase).

Bleeding score will be listed for each subject. Bleeding events and the number of subjects experiencing any bleeding episode will be summarized by panel.

Pharmacokinetic Analyses

PK parameters will be summarized by treatment. Geometric means and coefficients of variation will be presented for C_{max} (after dose 1 and dose 6), AUC(TAU), CLT, and C_{trough}. Additionally, scatter plots of C_{max} versus dose will be provided to assess the dependency on dose. A statistical analysis using a power model will be applied to assess dose proportionality.

Immunogenicity Analyses

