8.4.2 Efficacy Analyses

Platelet count and change from baseline and fold change from baseline will be listed for all treated subjects and summarized by panel and visit. Response status will be reported together with time to respond, time to peak response, and duration of response. Response rate will be provided by panel and treatment phase (response phase or remission phase). Different efficacy criteria will be used to evaluate each subject's responding status.

Bleeding score will be listed for each subject. Bleeding events and the number of subjects experiencing any bleeding episode will be summarized by panel.

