6.2 Treatment Groups

Treatment groups will be decided by the planned starting dose regardless of intra-subject dose escalation planned at day 57. Table 6.2-1 below indicates the planned treatment groups.

All summaries, except PK summary, will be provided by treatment group. For PK summary, it is current dose that is used to decide the dose group.

Table 6.2-1: Treatment Group

Cohort	Treatment Group Label
A	BMS 75mg
B	BMS 225mg
C	BMS 675mg
D	BMS 1500mg

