7.2 Study Conduct

Relevant deviations from the study protocol, protocol amendments and administrative changes will be documented and accounted for in presenting the data summaries, listings and descriptive statistical analyses. Deviations of protocol-specified inclusion and exclusion criteria will be listed. Any changes from planned protocol-specified analysis will be defined in the SAP and reported in the CSR.

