7.5.1 Derivation of Efficacy Endpoints

Primary efficacy criteria and response category:

- Response (R) - platelet count $\geq 30,000/\text{mm}^3$ and at least 2-fold increase from the baseline count and absence of bleeding.
- Complete Response (CR) - platelet count $\geq 100,000/\text{mm}^3$ and absence of bleeding.
- No Response (NR) - platelet count $< 30,000/\text{mm}^3$ or less than 2-fold increase of baseline platelet count or bleeding.
- Not Assessable (NA) - platelet count is missing or is excluded due to rescue medication.

Subject's best response is decided in the order of CR, R, NR, and NA.

Secondary efficacy criteria and response category:

- Clinically Significant Response - platelet count $\geq 50,000/\text{mm}^3$ with an increase of at least $20,000/\text{mm}^3$ from baseline and absence of bleeding.
- No Clinically Significant Response - platelet count $< 50,000/\text{mm}^3$, or increase of $\leq 20,000/\text{mm}^3$ from baseline, or bleeding.
- Not Assessable (NA) - platelet count is missing or is excluded due to rescue medication.

Absence of bleeding:

Absence of bleeding is defined as SMOG scores being zero for all the three major domains (Skin, visible mucosae, and organs) with ITP-BAT on the same day when platelet count is assessed.

Platelet data exclusion and rescue medication flag:

Platelet counts collected within 4 weeks after any rescue medication, though still shown in listing of figures of raw data, will be excluded from summarizing platelet and deriving subject response. To facilitate the exclusion, rescue medication flag may be derived and included in some analysis datasets and listings if at least one subject takes rescue medication after the first dosing during the trial. Rescue medication flag is set to Y (Yes) within 4 weeks after the day any rescue medication is administered, i.e., between rescue medication day and rescue medication day + 27, inclusively. It will be set to N (No) when otherwise.

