7.5.4 Response with primary efficacy criteria

The best response status over the entire study will be reported for all treated subjects with platelet at baseline, administered dose on day 1, and administered dose on day 57. For responders, treatment group, dose escalation status (Y/N), time to respond, time to peak response, and duration of response will be provided in a listing.

Response rates and number of subjects having dose escalated will be provided for each treatment group and all.

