7.5.5 Response under secondary efficacy criteria

Overall response rates during the whole study will be provided for each treatment group and all.

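### The SAP drops the protocol's treatment-phase split, so responses first reached after the Day 57 dose escalation are credited to the lower starting dose

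*SAP*

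**What the plan says.** Protocol 8.4.2 reads: "Response rate will be provided by panel and treatment phase (response phase or remission phase"). The synopsis says the same by cohort: "Response rate will be provided by cohort and treatment phase (response phase or remission phase").

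The SAP differs on three points.

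- **Group.** Section 6.2: "Treatment groups will be decided by the planned starting dose regardless of intra-subject dose escalation planned at day 57". This applies to every summary except PK.
- **Window.** Section 7.5.4 opens with "The best response status over the entire study will be reported for all treated subjects" and ends with "Response rates and number of subjects having dose escalated will be provided for each treatment group and all". Section 7.5.1 gives one ranking per subject: "best response is decided in the order of CR, R, NR, and NA". Section 7.5.5, on the secondary criteria, is explicit: "Overall response rates during the whole study will be provided for each treatment group and all".
- **Departures.** Section 7.2: "Any changes from planned protocol-specified analysis will be defined in the SAP and reported in the CSR". No change to the phase split is declared.

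Under SAP 2.1 and protocol 3.1.1, subjects without a clinically significant response at Days 43 and 50 may receive the next higher dose from Day 57.

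**The concern.** The first four doses are given at the starting dose. From Day 57, an escalated subject in the 75, 225 or 675 mg panel is on a different dose. A whole-study best response grouped by starting dose therefore combines two doses and credits the result to the lower one. The 1500 mg panel has no escalation, so the distortion runs one way: it raises the lower panels relative to the top.

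The problem is clearest in SAP 7.5.5. The criterion tabulated there (at least 50,000/mm³, a rise of at least 20,000/mm³, no bleeding) is the one whose failure triggers escalation. For R/CR in 7.5.4 the overlap is partial, because a subject already in R but below 50,000/mm³ can also be escalated.

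Evaluating efficacy by R/CR and establishing dose response are both secondary objectives. Elsewhere the SAP allows for the dose change: PK is summarised by current dose (6.2, 7.7.1), and escalated subjects are removed from the Day 71 dose-proportionality analysis (7.7.3). Response rates get no comparable treatment.

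**Working it through.** **Inputs from the documents.** Protocol Appendix 2 gives assumed response rates r = 0.20, 0.40, 0.55, 0.70 at 75, 225, 675, 1500 mg, and conditional response rates for non-responders after titration c = 0.25, 0.25, 0.33. Panel size is 10.

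**Reproducing the plan's figures.**
- Least squares of logit(r) on log(dose/75) gives intercept -1.33 and slope 0.72, matching the Appendix 2 prior mean.
- The exact (Clopper-Pearson) 90% interval for 4/10 is 0.150-0.696, matching the (0.15, 0.70) in protocol 8.1.
- (r_next - r)/(1 - r) = 0.20/0.80, 0.15/0.60, 0.15/0.45 = 0.25, 0.25, 0.333, matching c. The conditional rates are thus the step to the next dose's assumed rate.

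**Whole-study rate by starting dose.** Let e be the share of non-responders escalated and L the chance of late conversion on an unchanged dose.

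- Below 1500 mg: r + (1 - r)(e·c + (1 - e)·L)
- At 1500 mg: 0.70 + 0.30·L

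Appendix 2 implies e = 1 and L = 0: it has non-responders titrated and assumes that further dosing at the same dose converts no one. Then:

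- 75 mg: 0.20 + 0.80 × 0.25 = 0.400
- 225 mg: 0.40 + 0.60 × 0.25 = 0.550
- 675 mg: 0.55 + 0.45 × 0.33 = 0.6985
- 1500 mg: 0.700

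The 75-to-1500 mg spread falls from 0.50 to 0.30 and the log-odds slope from 0.724 to 0.4445. Per 10 subjects a panel, responders credited from the next dose number 2.0 + 1.5 + 1.485 = 4.985 of an expected 23.485.

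**Sensitivity.** The documents give no range for e or L. The values below 1 for e and above 0 for L are assumptions.

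| e | L | 75 mg | 225 mg | 675 mg | 1500 mg | Spread | Slope |
|---|---|---|---|---|---|---|---|
| Starting dose only | – | 0.200 | 0.400 | 0.550 | 0.700 | 0.500 | 0.724 |
| 1 | 0 | 0.400 | 0.550 | 0.699 | 0.700 | 0.300 | 0.444 |
| 1 | 0.10 | 0.400 | 0.550 | 0.699 | 0.730 | 0.330 | 0.486 |
| 1 | 0.25 | 0.400 | 0.550 | 0.699 | 0.775 | 0.375 | 0.553 |
| 0.8 | 0 | 0.360 | 0.520 | 0.669 | 0.700 | 0.340 | 0.491 |
| 0.8 | 0.10 | 0.376 | 0.532 | 0.678 | 0.730 | 0.354 | 0.512 |
| 0.8 | 0.25 | 0.400 | 0.550 | 0.691 | 0.775 | 0.375 | 0.549 |
| 0.5 | 0 | 0.300 | 0.475 | 0.624 | 0.700 | 0.400 | 0.568 |
| 0.5 | 0.10 | 0.340 | 0.505 | 0.647 | 0.730 | 0.390 | 0.553 |
| 0.5 | 0.25 | 0.400 | 0.550 | 0.681 | 0.775 | 0.375 | 0.543 |

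Over all nine combinations the 75 mg rate is 0.30-0.40 (against 0.20), the spread 0.30-0.40 (against 0.50) and the slope 0.44-0.57 (against 0.72). At L = 0.25 late conversion equals the titration rate at 75 and 225 mg, so the shift there reflects the longer window rather than the dose. A phase split exposes either effect.

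**Precision.** The exact 90% interval is 0.04-0.51 for 2/10 and 0.15-0.70 for 4/10, so sampling error in one panel is larger than the shift.

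**The case against.** **Version lag.** The SAP reflects Amendment 02, with a 4-week follow-up and no long-term extension. The supplied protocol has 8 weeks and an extension, so it appears to be later. The Amendment 02 wording of 8.4.2 is not available. An undeclared departure from the version then in force is therefore unproven. What stands is that the two documents now disagree.

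**Window in 7.5.4.** The rate sentence names none. Whole study is the likely reading from the sentence before it and from 7.5.1, but it is an inference; only 7.5.5 states it. Parts of the SAP (7.8, 7.10) are redacted and table details are left to the Data Presentation Plan, so only the visible SAP can be judged.

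**Starting-dose grouping is the protocol's own.** Reporting by panel would keep a post-escalation response under the starting panel in the Remission Phase too. That is correct. The phase split at least isolates Response Phase response, when every subject is still on the starting dose. A further split by escalation status goes beyond 8.4.2.

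**Size.** Appendix 2 does not name its response criterion, and its conditional rates restate the next dose's rate. Best response within the Response Phase would also count transient responses lost by Days 43 and 50. If 10-25% of Appendix 2 non-responders had one (an assumption), the Response Phase slope would itself be 0.63-0.53, and the escalation shift at 75 mg would be 0.18-0.15 rather than 0.20. This changes the size, not the direction.

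**Mitigation.** The SAP gives the number escalated beside the rates. It lists both doses, escalation status, time to response and response category by day, so with 10 subjects a panel the split could be rebuilt. By-day platelet summaries before the Day 57 dose are unaffected. Protocol 8.5 and Appendix 2 describe separate dose-response models. The primary objective is safety and there is no formal hypothesis. All of this limits the consequence, but the visible SAP still does not plan the table that the protocol specifies.

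**Conclusion.** The concern holds and should be fixed. The visible SAP omits the phase split of protocol 8.4.2 and, followed as written, credits post-escalation responses to the lower starting dose. This is explicit for the secondary criteria and the likely reading for R/CR. Such rates are legitimate as response under the escalation strategy; read as dose-specific rates, they overstate the lower doses and tend to flatten the dose response.

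On the Appendix 2 rates with all R/CR non-responders escalated and no late conversion, the 75 mg rate doubles and 675 and 1500 mg become almost equal (0.6985 and 0.700). Under the wider assumed ranges the slope loses less but stays below 0.72 throughout. These figures are illustrative, and confidence is medium given the version gap and the redactions.

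A minor, separate point: SAP 4.1 uses PR and disease progression, neither defined in the visible documents, whereas protocol 5.4.2 ends duration at loss of CR or R. This affects a listing only.

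**What to change.** In SAP 7.5.4 and 7.5.5, add the panel-by-phase response table:

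1. **Response Phase response by starting dose**, from assessable counts after the Day 1 dose and before the Day 57 dose. State the cut-off as a choice: the protocol calls this phase 6 weeks but evaluates response through Day 50, and a strict Day 43 cut would drop the Day 50 count.
2. **Remission Phase response by panel and escalation status (Y/N)**. The second split is an addition to 8.4.2, needed because panel alone still mixes doses. State where follow-up counts belong.
3. **Whole-study best response by starting panel**, kept as a supplementary summary and labelled as response under the escalation strategy.

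If the phase split was dropped on purpose, declare it with its reason under SAP 7.2. In SAP 4.1, replace PR with R and disease progression with loss of CR or R, and say how counts made Not Assessable by rescue medication enter duration.

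The cost is SAP wording and a split of tables already planned. No new data are needed.

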1.3.2 Secondary Objectives

- To evaluate efficacy of BMS-986004 in the treatment of thrombocytopenia in subjects with chronic ITP, as measured by platelet response/complete response (R/CR) and other clinical parameters.
- To establish BMS-986004 dose response, as measured by platelet count and other clinical parameters.
- To measure the target engagement of BMS-986004 following multiple IV doses
- To assess the effect of BMS-986004 on markers associated with the risk of thromboembolism (TE) in the multiple dose setting
- To assess pharmacokinetics and immunogenicity of multiple doses of BMS-986004 in subjects with chronic ITP.

[REDACTED]

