8 STATISTICAL CONSIDERATIONS

8.1 Sample Size Determination

The number of subjects is not based on statistical power considerations. If 4 responders are observed out of 10 subjects at a dose level, a 90% confidence interval for the response rate is (0.15, 0.70).

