- Extremely small probability for β_2 being negative

It is assumed that the response rate at dose of 75mg, 225mg, 675mg, and 1500mg to be 0.2, 0.4, 0.55 and 0.7 respectively. A linear regression using the above data will give prior mean μ to be (-1.33, 0.72) with rounding error. The second and third bullets of the guidelines would make the stand deviation of β_1 to be 0.45, and β_2 to be 0.2. Prior distributions of β_1 and β_2 are assumed to be independent. A 95% credible interval of response rates under prior and without observation data is shown in Figure 1, where the top curve is the upper 97.5% quantile, the center is the mean, and the bottom is the lower 2.5% quantile. The circles represent the expected response rates at the selected doses. It can be seen that the chosen prior would lead to a mean response rate estimate being very close to the expected or assumed, and at the same time the wide region of 95% credible interval indicates that the prior's weak impact on the posterior estimation of response rate when data are observed.

Figure 1: 95% Credible Interval of Response Rate under Prior Only

Special consideration for titration

Non-responders at each cohort other than the maximum 1500mg cohort would be administered higher dose with the hope of becoming responders. Therefore, two response status data may be observed for those non-responders. Due to relative small sample size of each cohort, making use of status data after the titration dose is believed to increase the accuracy of model-based prediction under some reasonable assumptions. Listed in the below are two assumptions used in the adaptive dose selection:

- If a subject responds to a dose, the subject would respond to higher dose with probability 1.

- If a subject does not respond to a dose after 3 administrations, additional dosing at the same dose would not make a subject change from non-responder to responder.

Based on the above assumptions, a new approach is proposed to combine the subjects at two adjacent cohorts to estimate the response rate at the higher dose which is shared by the two cohorts.

Simulation

Trial simulation is done to show the performance of logistic regression and Bayesian logistic regression with starting dose data only or with titration data included. The Settings of simulation parameters are listed below for convenience:

[figure not shown]
- Doses: 75, 225, 675, 1500
- Rate: 0.2, 0.4, 0.55, 0.7

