- Conditional response rate for non-responder after titration: 0.25, 0.25, 0.33
- Response rate used to predict dose: 0.7 (equivalently the fourth cohort)
- Number of simulated trials: 1000

Prediction results from four different methods are compared with each other.

- SLogit: Logistic regression with response status from starting dose only
- SBayLogit: Bayesian logistic regression with response status from starting dose only
- DLogit: Logistic regression with response status from both starting dose and titration dose
- DBayLogit: Bayesian logistic regression with response status from both starting dose and titration dose

Simulation results are shown in Figure 2. It can be seen that Bayesian modeling provides less variant and seemingly closer-to-true-value predictions compared to the usual logistic regression. In addition, variation of the predicted dose is smaller by including titration data when same modeling is used.

Figure 2: Predicted Dose from Different Methods

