2 STUDY DESCRIPTION

2.1 Study Design

This is a Phase 1b/2, multicenter, open-label, MAD study to evaluate the safety, efficacy, dose response, and pharmacology (PK, target engagement and PD) of BMS-986004 administered every 2 weeks in subjects with ITP.

Figure 2.1-1: Study Design Schematic

[figure not shown]
The study is divided into screening (3 weeks), response phase (6 weeks), remission phase (6 weeks) and follow up period (4 weeks). Forty subjects are treated in 4 dose panels, 75mg, 225mg, 675mg, and 1500mg, of 10 subjects each. BMS-986004 will be administered on day 1, 15, 29, 43, 57, 71, 85, a total of 7 doses as IV infusion. Four (4) doses will be administered during the Response Phase over a 6 week treatment period. The remaining 3 doses will be administered during the Remission Phase of the study over a 6 week treatment period. The study design schematic is presented in Figure 2.1-1.

Cohort of lower than 75mg or intermittent dose may be opened.

Intra-subject dose escalation

Subject may be dosed at a higher dose beginning from day 57 for the remainder of the study if clinically significant response has not been achieved at Day 43 and Day 50, and a favorable safety profile is observed.

Figure 2.1-2: Decision Rule on Intra-Subject Dose Escalation

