7.1 General Methods

All data recorded on case report forms will be listed by subject. Descriptive summaries will be presented for continuous variables using number of subjects (N), mean, standard deviation (SD), median, minimum and maximum. Geometric mean and coefficient of variation (%CV) will also be presented for sample serum concentration-time data and PK parameters. Descriptive summaries for categorical variables will utilize counts and percentages.

Adverse events and medical history will be coded according to the most recent Medical Dictionary for Regulatory Activities (MedDRA). Previous and concomitant medications will be coded using the WHO Drug Dictionary.

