7.5.3 Platelet Count

Bleeding SMOG score, platelet count, platelet change from baseline, potentially rescue medication flag, and response category (each under primary and secondary efficacy criteria) at each study day will be listed for all treated subjects.

Platelet count and change from line will be summarized by treatment group for each study day. Percent of visits with platelet count $\geq 30,000/\text{mm}^3$, $50,000/\text{mm}^3$, and $100,000/\text{mm}^3$ will be listed for each subject and summarized for each treatment group.

Platelet count and its change from baseline may be explored by graphs and statistical models. Details are available in the section of exploratory biomarker analysis.

Exploratory analysis of platelet count is shown in section 0.

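### SAP 7.5.4 and 7.5.5 report whole-study response by starting dose with no interval and no analysis across doses, which blurs the dose response that the study sets out to establish

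*SAP*

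**What the plan says.** Dose response is a secondary objective in both documents: "To establish BMS-986004 dose response, as measured by platelet count and other clinical parameters" (protocol 1.3.2, repeated in SAP 3.2). The first efficacy endpoint in SAP 4.1 is response rate.

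SAP 7.5.4 takes each subject's best status across the whole study and commits to this output: "Response rates and number of subjects having dose escalated will be provided for each treatment group and all". SAP 7.5.5 does the same for the secondary criteria, with overall rates for the whole study. SAP 6.2 assigns every subject to the starting-dose group whatever happens at Day 57. On form, SAP 7.1 says "Descriptive summaries for categorical variables will utilize counts and percentages".

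The protocol differs in two ways. Section 8.4.2 asks for response rate by panel and by treatment phase (response or remission). Section 8.1 describes precision by an interval: with 4 responders of 10, "a 90% confidence interval for the response rate is (0.15, 0.70". SAP section 5 does not carry that interval over, and no visible response section commits to one.

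Modelling is mentioned in two other places. SAP 7.5.3 says "Platelet count and its change from baseline may be explored by graphs and statistical models", which is optional and concerns platelet count. Protocol 8.5 and Appendix 2 describe logistic models of response on log dose, used to choose the doses of later cohorts.

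**The concern.** Two gaps work together. First, nothing in the visible response sections relates response to dose or shows how uncertain a rate on 10 subjects is. Second, the endpoint itself mixes doses. A subject who does not respond on 75 mg, is escalated, and then responds on 225 mg is counted as a responder in the 75 mg group. The top cohort has no higher dose to move to. The lower cohorts are therefore lifted and the top one is not, which compresses the gradient.

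A true monotone dose response could then appear in the report as four irregular or nearly flat percentages, with nothing to show how compatible they are with a rising curve. In a dose-finding study that reading could influence the choice of dose for later work.

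**Working it through.** **Inputs**
- Cohorts (SAP 2.1): "Forty subjects are treated in 4 dose panels, 75mg, 225mg, 675mg, and 1500mg, of 10 subjects each".
- Starting-dose rates (protocol Appendix 2): "It is assumed that the response rate at dose of 75mg, 225mg, 675mg, and 1500mg to be 0.2, 0.4, 0.55 and 0.7 respectively".
- After escalation (protocol Appendix 2): "Conditional response rate for non-responder after titration: 0.25, 0.25, 0.33".
- Significance level: none is stated for response. I assume 5% and show one-sided and two-sided results.

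**1. The plan's own figures.** The exact Clopper-Pearson 90% interval for 4/10 runs from the 5% quantile of Beta(4, 7) to the 95% quantile of Beta(5, 6), which is (0.150, 0.696). This matches the protocol's (0.15, 0.70). Wald (0.145, 0.655) and Wilson (0.194, 0.648) do not. The Appendix 2 prior mean also reproduces: a straight line through logit(rate) on log(dose/75) gives (-1.325, 0.724), against the stated (-1.33, 0.72).

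**2. What whole-study best response does to the rates.** For a cohort with starting-dose rate p and post-escalation rate q among non-responders, the expected whole-study rate is p + (1 - p)q:
- 75 mg: 0.20 + 0.80 × 0.25 = 0.40
- 225 mg: 0.40 + 0.60 × 0.25 = 0.55
- 675 mg: 0.55 + 0.45 × 0.33 = 0.6985
- 1500 mg: no escalation, 0.70

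**3. Effect on the slope.** With x = log(dose/75) = 0, 1.099, 2.197, 2.996, the mean is 1.573 and Σ(x - 1.573)² = 5.113. The deviations are -1.573, -0.474, 0.624 and 1.423. The least-squares slope of the logits is Σ(x - 1.573)·logit / 5.113.
- Starting dose: logits -1.386, -0.405, 0.201, 0.847. Slope = (2.180 + 0.192 + 0.125 + 1.205)/5.113 = 0.72.
- Whole study: logits -0.405, 0.201, 0.840, 0.847. Slope = (0.637 - 0.095 + 0.524 + 1.205)/5.113 = 0.44.

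**4. How the four percentages would look.** I enumerated all 11⁴ = 14,641 possible responder counts with binomial weights and summed those in which the four observed rates are not in non-decreasing order.

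**5. What one trend analysis could recover.** The Cochran-Armitage statistic on log dose is Z = Σ yᵢ(xᵢ - x̄) / √[p̄(1 - p̄) × 10 × 5.113], where yᵢ is the number of responders in cohort i and p̄ the pooled rate. Power is the total probability of the rejecting outcomes over the same enumeration.

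| | Starting-dose response | Whole-study best response |
|---|---|---|
| Expected rates | 0.20/0.40/0.55/0.70 | 0.40/0.55/0.70/0.70 |
| Observed rates out of order | 43.6% | 65.7% |
| Trend power, one-sided 5% | 79.4% (exact conditional 77.4%) | 47.1% (44.0%) |
| Trend power, two-sided 5% | 68.2% (66.4%) | 34.6% (33.1%) |

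The asymptotic test has a true one-sided size of 5.2% at a common rate of 0.4. A two-sided logistic regression, checked by simulation on the starting-dose rates, has 65.7% power (Wald) or 69.8% (likelihood ratio), in line with the table.

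**The case against.** **The study is descriptive.** Protocol 1.2 states no formal hypothesis, 8.1 does not base the sample size on power, and 8.5 plans no inference that needs adjustment. This stands against a demand for a test. It does not stand against an interval or a slope, which are estimates. SAP 7.7.3 already gives a 90% interval for the dose-proportionality slope, and it drops escalated subjects from the Day 71 analysis because their dose has changed.

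**The objective names platelet count.** It does, together with other clinical parameters, and SAP 7.5.3 summarises platelet count by group and study day. But response rate is the named efficacy endpoint, and the modelling in 7.5.3 is optional.

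**A model may exist elsewhere.** Appendix 2 sets out a log-dose logistic model and refers to further discussion in the SAP, and SAP 7.8 and 7.10 are redacted. A reader might infer that the plan has no dose-response analysis at all, and the documents cannot support that. What can be said is that the visible response sections have none, and that the Appendix 2 model serves to pick doses rather than to report results.

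**Low-powered comparisons.** A reader might infer that the objective rests on cohort comparisons with 8-13% power. No such comparisons are planned. That range comes from one-sided Fisher tests of adjacent doses only (13.0%, 8.6%, 8.5%), and the same test of 75 v 1500 mg has 62%. Matching test types also changes the gap: adjacent z tests have 18-25% against 79% for the trend, and adjacent exact tests 8-13% against 77%.

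**The comparison favours the trend.** The Appendix 2 rates lie close to a line in logit against log dose, so a log-dose trend suits them. That is fair, and it limits how far the figures generalise.

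**Conclusion.** The point holds for the visible response sections. For response, the dose-response objective is left to informal comparison of percentages on 10 subjects each, and the chosen window pulls those percentages together. At the protocol's own rates the log-odds slope drops from 0.72 to 0.44, the chance of an out-of-order picture rises from 44% to 66%, and trend power falls from 79% to 47% one-sided (68% to 35% two-sided).

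It would be wrong to read the 79% as the gain from adding a trend test to SAP 7.5.4 as it stands. On that endpoint the figure is 47%. The higher power depends on also restricting response to the period before escalation.

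The figures assume that the Appendix 2 rates are true, that the planned doses are unchanged with 10 subjects per cohort, that every starting-dose non-responder below 1500 mg is escalated, and that a starting-dose responder stays counted as a responder. The change is worth making, but the gap is a missing analysis and missing intervals. It is not a planned test that fails.

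**What to change.** In SAP 7.5.4:
1. Report response by treatment phase, as protocol 8.4.2 states. The whole-study best response can stay as an additional summary.
2. Give an exact (Clopper-Pearson) 90% confidence interval with each cohort's rate, the same method that reproduces the protocol 8.1 figure.
3. Prespecify one logistic (or Cochran-Armitage) trend on log starting dose, using response before any escalation (through Day 50). Enter the starting dose actually used if a later cohort's dose has been adapted. Report the slope with its 90% interval and label it as estimation, not a formal test.

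If a redacted section already contains such a model, a cross-reference from 7.5.4 and a statement of the response window would be enough for item 3.

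The cost is a few lines of SAP text and code, with no new data. The drawback is that the slope assumes a monotone, roughly log-linear relation. The cohort rates and intervals should therefore be shown beside it, so that a plateau or reversal remains visible.
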